Quantitative Sensory Testing (QST) Measures of Laboratory Evoked Pain: Subjects will complete a state-of-the-art quantitative sensory testing (QST) battery, which will comprehensively and systematically measure pain sensitivity. This approach will provide information regarding the full range of analgesic effects possible, across a wide variety of psycho-physiologically-mediated, experimentally-induced measures of pain perception. Subjects will complete a baseline QST session prior to study drug administration on each experimental session day, and will complete the pain testing battery at regular intervals during the experimental session day. Each administration of the QST battery will take 20-30 minutes. The QST battery will consist of threshold and tolerance, temporal summation, and conditioned

pain modulation (CPM) tests. The threshold responses will be conducted in randomized and counter-balanced order, and conditioned pain modulation will always occur last.

Threshold Responses will be assessed using thermal and pressure stimulation. *Thermal threshold:* All contact heat stimuli will be delivered using a peltier-element-based stimulator (Medoc, Israel). Two trials of heat pain threshold will be administered using an ascending method of limits paradigm. The thermode will gradually increase in temperature (rate of rise = .5°C/sec) from a pre-set baseline (31°C), until the subject indicates when the stimulus “first feels painful” (threshold, HPT_h) and presses a button (which terminates the procedure) indicating that the pain is intolerable (tolerance, HPT_o). *Pressure threshold:* A pressure algometer will be utilized to assess responses to pressure stimulation at a variety of anatomical sites in a randomly determined order. The pressure algometer (Somedic; Sweden) uses a rubber probe covered with 1mm polypropylene material; pressure at the site is gradually increased at a steady rate. Subjects indicate when the stimulus is first perceived as painful, which terminates the application. The algometer produces a sensation of localized pressure; technicians will place the probe of the algometer in the center of each muscle group or anatomic site when delivering the mechanical stimuli. Thirty-second inter-stimulus intervals will be maintained for all stimuli. Each trial will be averaged together to result in one HPT_h, HPT_o, and PPT_h measure.

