Cold Pressor Testing and CPM: A series of procedures designed to elicit and measure endogenous inhibition of pain will be applied. In the present protocol, subjects will undergo a series of cold pressor tasks (i.e., the conditioning stimuli) consisting of immersion of the hand for up to 1 minute in a circulating cold water bath. During hand immersion, pressure responses or temporal summation will be re-assessed while subjects’ hands remain in the cold water. Subjects may remove their hand at any time. Two minutes after finishing the first immersion, subjects will re-immerses their hand in the water, and one of these tests will be re-assessed, each separated by 2 min and identical to the first 2 trials (the tests will be conducted in random order). CPM Index is quantified as the average percent change (across trials) in PPT_h or TS during the cold pressor tasks relative to baseline ratings [(PPT_h or TS during cold pressor/PPT_h or TS prior to cold pressor)*100].¹⁰¹ One final cold-water immersion will be performed at the conclusion of the CPM procedures. This will involve a typical cold pressor task, using immersion of the hand until the subject’s tolerance is reached, with a 5-minute uninformed time limit.

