- **Primary Aim 1:** The primary outcome will be the area under the curve of each QST procedure, which will provide an assessment of the mean duration and magnitude of the drug effect. Primary outcomes will be tested with repeated two-factor (Drug Condition x Time) models to examine main and interaction effects for all raw data as designed. If there is large variation across subjects at the baseline timepoint, the raw data will be transformed as a change from baseline and analyzed in drug condition by time models. Statistical analyses will be conducted using multilevel analyses with an autoregressive covariance structure using SAS PROC MIXED Software¹³¹. These analyses will permit an examination for effects of drug condition and time effects associated within the course of the study. Interpretation of drug condition main effects and interactions will rely on Tukey post-hoc tests. This aim will also assess frequency of adverse events as a function of study drug.

Specific outcome variables for the QST procedures will be as follows:

- a. Heat Pain Threshold and Tolerance: HPT_h and HPT_o in °C (both in normal and capsaicin treated skin)
 - b. Pressure Pain Threshold: PPT_h in kilopascals
 - c. Thermal and Mechanical Temporal Summation: Verbal pain ratings (both in normal and capsaicin treated skin for MTS)
 - d. Conditioned Pain Modulation: The index score of CPM:PPT_h and CPM:TS (compared to baseline) for each dose
 - e. Cold Water Tolerance: Time to tolerance (compared to baseline) for each dose.
- **Primary Aim 2:** The Drug vs. Money questionnaire will be compared across dose conditions, using peak monetary rating for each dose as the primary outcome. Within-subject changes, as a function of dose, will be analyzed using a repeated measures analysis of variance (ANOVA).
 - **Primary Aim 3:** Neurocognitive tests will be compared as a function of study drug dose, using study session number (1-6) as a covariate to control for practice effects. Specific outcome measures will include:
 - a. Divided Attention Task (DAT): Accuracy with which they perform the two tasks
 - b. Digit Symbol Substitution Task (DSST): Accuracy, total number of patterns completed in allotted time
 - c. Computerized version of the Paced Auditory Serial Addition Task (PASAT): Summed of correct trials

b. Secondary outcome variables.

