among patients undergoing opioid withdrawal (of which increased heart rate and blood pressure is a known symptom) and who received a dose of dronabinol (40mg) that is double the highest potential dose proposed here (20mg). These effects were diminished when the dronabinol dose was reduced to 30mg (132). Though we do not believe this study completely corresponds to our laboratory design, which is enrolling healthy individuals who are not otherwise predisposed to elevated blood pressure and heart rate and who are receiving doses of dronabinol that are lower than those administered in the prior study, we are sensitive to this potential outcome. To address this, we will monitor vital signs at all study data collection time points and will follow procedures that we have developed and successfully used in previous studies that administered drugs (e.g., cocaine) with known cardiovascular risks. Specifically, if a participant's parameters reach these thresholds, then a study physician, who will always be available via telephone, will be contacted and consulted to determine the appropriate course of action.

- Systolic blood pressure: ≥ 180 mm Hg
- Diastolic blood pressure: ≥ 120 mm Hg
- Heart Rate: \geq submaximal heart rate ($220 - [\text{age} \times 0.85]$).

Appropriate courses of action may include observing the participant until the parameters return to normal or transferring the participant to the Emergency Department (ED). Our research unit, which is the location in which all study sessions will be conducted, is located across the street from the Johns Hopkins Bayview Medical Center (JHBMC) ED. Participants who can walk will be escorted to the ED by a study staff member. If there is any question in a participant's ability to walk safely then 911 will be called to have an ambulance dispatched for the participant.

Additional stopping rules will include not abiding by the BPRU policies and procedures, or engaging in behaviors towards staff or other participants that are abusive. Finally, development of an intercurrent illness or condition that changes the participants risk may result in medical discharge from the study.

8. Risks

- a. Medical risks, listing all procedures, their major and minor risks and expected frequency.

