
Participants will also not be informed about the specific medication they are receiving, which is a common procedure used by our research unit to minimize bias in responding. This procedure also makes it difficult for the

participant to seek out drugs they may have found reinforcing during the study session, thus further minimizing the opportunity for study participation to increase risk of non-study drug abuse.

d. Protection Against Risks of Discomfort from Pain Testing: It is likely that participants will experience some acute and transient discomfort from the pain testing session, however we will work to mitigate that risk as much as possible. First, participants will be informed of the pain testing procedure during the informed consent and will be able to make an informed decision regarding their study participation. Second, we chose standardized pain tests that are known to produce short-lived effects and thus are unlikely to produce any residual pain. Third, the measures rely on the participant ending the pain testing procedure as an outcome measure, which means that all participants are encouraged to remove themselves from the painful stimulus at any time and that they are in control of the magnitude and duration of pain they experience. Fourth, we will enforce an upper limit on both pain measures to prevent any tissue damage from occurring (e.g., hand cannot be in cold presser task for >150 seconds). Fifth, participants will be informed that they can revoke their consent to participate in the pain testing at any time without penalty. Finally, the participants will be monitored 24 hours by study staff and will have access to medical care and concomitant medications to treat residual pain if necessary. We will also document and review all adverse events reported from the pain testing session and will follow any recommendations they may have regarding the cessation of pain testing.

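### Section 4 allows the final cold-water immersion to run 300 s, twice the 150 s limit that section 8 says will be enforced to prevent tissue damage

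*Combined protocol and SAP*

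**What the plan says.** Section 4.a (Cold Pressor Testing and CPM) describes two kinds of immersion. The conditioning immersions are a series of tasks "consisting of immersion of the hand for up to 1 minute in a circulating cold water bath". After them comes one further immersion that continues until the participant can no longer tolerate it, "with a 5-minute uninformed time limit".

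Section 8.b, item d (protection against discomfort from pain testing) lists several safeguards. The third is that the participant controls when a test ends. The fourth is that "we will enforce an upper limit on both pain measures to prevent any tissue damage from occurring", with the example "hand cannot be in cold presser task for >150 seconds".

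Section 4.a (Quantitative Sensory Testing) has participants do a baseline battery in each session and says they "will complete the pain testing battery at regular intervals during the experimental session day". Section 7.a, Primary Aim 1, item e names the resulting outcome: "Cold Water Tolerance: Time to tolerance (compared to baseline) for each dose".

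**The concern.** Both limits are current text, both concern the cold pressor, and they differ. A participant whose hand is still in the water between 150 s and 300 s is within section 4 and in breach of section 8. The participant is not told of the 5-minute limit, so only staff can apply it, and the procedure section that directs them gives the longer figure.

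The exposure recurs: the immersion closes the battery at baseline and after dosing. Four of the five sessions in the dosing table (section 6.a) give hydromorphone 4 mg, an analgesic that the study expects to lengthen tolerance.

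There is also a measurement problem. Time to tolerance is right-censored at whichever limit staff use. If some stop at 150 s and others at 300 s, the same response is recorded with different maxima.

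**Working it through.** **1. The conflict itself.** Section 4: 5 min × 60 = 300 s. Section 8: 150 s. Ratio 300/150 = 2; excess 300 − 150 = 150 s. No modelling is needed for this step.

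**2. Could the 150 s refer to a different immersion?** The only other cold immersions are the conditioning ones, capped at 60 s. A 150 s limit could never bind on them, so it binds only on the tolerance immersion.

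**3. How many immersions.** The number of post-dose batteries is not stated; I assume at least 2. Then 5 sessions × (1 + 2) = 15 per participant, and 15 × 60 completers = 900. Of each 15, 8 follow hydromorphone (4 sessions × 2). The other 7 are reference: 5 baseline and 2 post-dose in the placebo session.

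**4. How many might pass 150 s.** The documents give no tolerance times. I assume lognormal times with median 40, 60 or 90 s, log-SD 0.8 or 1.0, and a drug ratio of 1.3 on the median.

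Share past the cap = 1 − Φ(ln(150/median)/log-SD). Weighted share = (7 × reference + 8 × active)/15.

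| Median | log-SD | Reference | Active | Weighted | Of 900 |
|---|---|---|---|---|---|
| 40 s | 0.8 | 0.049 | 0.093 | 0.072 | 65 |
| 40 s | 1.0 | 0.093 | 0.145 | 0.121 | 109 |
| 60 s | 0.8 | 0.126 | 0.207 | 0.169 | 152 |
| 60 s | 1.0 | 0.180 | 0.257 | 0.221 | 199 |
| 90 s | 0.8 | 0.262 | 0.378 | 0.324 | 291 |
| 90 s | 1.0 | 0.305 | 0.402 | 0.357 | 321 |

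**5. What the cap does to the outcome.** Under the same assumptions, I compared the mean gain on drug with each time cut at the cap against the gain with no cap.

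| Median | Share of gain seen, 150 s cap | Share of gain seen, 300 s cap |
|---|---|---|
| 40 s | 57–75% | 81–94% |
| 60 s | 41–57% | 68–85% |
| 90 s | 27–37% | 53–70% |

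The standardised paired effect is mean difference divided by SD of the difference, from simulation with an assumed within-person correlation of 0.7 on the log scale. At median 60 s, for 150 s / 300 s / no cap, it is 0.38 / 0.36 / 0.31 (log-SD 0.8) and 0.29 / 0.29 / 0.21 (log-SD 1.0). The cap changes the effect in seconds but does not reduce the chance of detecting it.

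**6. Two neighbouring items in section 7.d, separate from the cold-pressor point.**

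- The heart-rate trigger is labelled "submaximal heart rate" but printed as 220 − (age × 0.85). That gives 220 − 15.3 = 204.7 bpm at age 18 and 220 − 63.75 = 156.25 at age 75. If maximal means 220 − age (my assumption), the maxima are 202 and 145, so the printed trigger lies above them. If (220 − age) × 0.85 was intended, the values are 171.7 and 123.25. The gap is then 220 − 187 = 33 bpm at every age.
- Section 7.d gives 20 mg as the highest dronabinol dose. The dosing table and section 6.b give 10 mg, so the margin to the cited 40 mg is 40/10 = 4-fold, not 2-fold.

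**The case against.** The strongest reply is that nobody holds the hand in the water. The immersion runs to the participant's own tolerance, and both section 4 and section 8 let participants stop at any time. That lowers the risk and should be acknowledged. It does not remove the conflict, because section 8 lists the enforced limit as a further safeguard, for those who do not withdraw.

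A second reply is that 150 s may be the stale number. It appears only as an example, without derivation, and section 8 speaks of two pain measures although the battery has many more. That is plausible. But then section 8, the current statement of participant protections, is the text that is wrong. One section has to change either way.

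Third, no injury is shown. That stands: the water temperature is not given, and the documents do not establish that 150 to 300 s is harmful. The point is only that the procedure permits a breach of the protocol's own limit.

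Fourth, the exposure counts rest on assumed inputs and span a five-fold range, and no loss of power follows. That also stands. The counts illustrate scale and are not needed for the conclusion. The heart-rate and dose items lend it no weight either; the heart-rate threshold leads to a telephone consultation with a physician, not an automatic action.

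**Conclusion.** The concern holds. Sections 4 and 8 set limits of 300 s and 150 s for the same immersion, nothing says which governs, and following the procedure can exceed the stated safety limit by up to 150 s. This rests on the text alone and should be corrected before staff work from section 4.

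The size of the exposure is uncertain: about 65 to 320 of at least 900 immersions past 150 s, given the assumed tolerance times, drug ratio and number of batteries. For the statistics, the consequence is an undefined censoring point for one of the five groups of Primary Aim 1 pain outcomes, affecting the effect expressed in seconds but not, under these assumptions, its detection.

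**What to change.** Amend section 4.a to 150 s, or have the medical team justify another single limit and correct section 8.b to match. State that it applies to every tolerance immersion, in every battery and session. This is a one-line amendment. The drawback of 150 s is that more trials end at the ceiling.

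Two inexpensive additions would help interpretation but are not needed to resolve the conflict: report the share of trials reaching the limit by drug condition, and add a censored-data analysis of time to tolerance as a sensitivity check. Neither needs extra data.

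Separately, ask the medical team to check the heart-rate formula in section 7.d against its label, and change the 20 mg there to 10 mg as an editorial correction.

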
Conclusion: This will be the 1st human laboratory study to evaluate combinations of cannabinoids and opioids on a comprehensive and validated quantitative sensory testing battery, and the results of this study will identify whether a signal for this medication combination exists that should be advanced into randomized controlled trial evaluations with clinical pain populations. This study will also assess aspects that would impact drug development (abuse liability, neurocognitive impairment) and the effect of participant sex on outcomes. The ultimate goal of this research will be to determine which medication/dose combinations may exert strong analgesic effects, while minimizing abuse liability and cognitive deficits, in order to advance these medications into clinical trials for the treatment of chronic pain. This is a logical first step towards evaluating combined cannabinoid/opioids treatments for chronic pain, and will provide data necessary to support numerous evaluations of combination treatments for this population.

4. Study Procedures

- a. Study design, including the sequence and timing of study procedures (distinguish research procedures from those that are part of routine care).

Project Overview: This study will enroll 100 healthy adults, and will aim to complete 60 (30 men, 30 women) participants. Participants will conduct a within-subject evaluation of the degree to which the FDA-approved cannabinoid dronabinol (Marinol) enhances the analgesic effect of the prototypic opioid hydromorphone (Dilaudid). Subjects will complete a Screening visit to establish study eligibility and 5 experimental sessions. Experimental sessions will occur approximately once weekly and will permit subjects to admit themselves into the clinical research unit the night before the session if interested. Subjects will be provided with taxi service to and from the session. Subjects will receive a dose of hydromorphone (4mg, oral) and a double-blind oral dose of study drug or placebo the

morning of each experimental session, and will undergo QST measures of laboratory evoked pain, provide self-report ratings of drug effects, and complete a neurocognitive battery. The order of sessions will be randomized with the exception of Session 1, which will always be active hydromorphone + placebo to ensure the participant has a safe response to hydromorphone before proceeding into the remaining sessions.

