- Discomfort Intolerance Scale: A 7-item self-report measure of tolerance to distressing situations.

Session Measures:

- Clinical Opiate Withdrawal Scale: A widely used, 11-item observer-rating of opioid withdrawal symptoms.
- Vital Signs: We will assess blood pressure, pulse, respiration, and oxygen saturation.
- Pupillary Diameter: Pupil size will be assessed using an electronic Neuroptics Pupilometer
- Visual Analog Rating Scales: Participants will rate the subjective reports of drug effects items on a scale of 0 (none at all) to 100 (strongest possible), including items such as good effects, bad effects, high, withdrawal, sick, like how I feel, nausea, sedation, feel sleepy.
- Opioid Agonist/Antagonist Rating Scale: This questionnaire assesses positive and negative effects of opioids.
- Drug vs. Money Questionnaire: This questionnaire is a frequently used measure to assess relative monetary value of a drug and is being used to assess relative reinforcing effects of the drug compared to hypothetical monetary values.

Computer-based Cognitive Tests:

- Divided Attention Task (DAT): Participants simultaneously perform two different simple tasks based on visual stimuli presented on a computer screen. This task is computer based.
- Digit Symbol Substitution Task (DSST): Participants must hand type patterns presented to them on a computer screen for 90 seconds
- Paced Auditory Serial Addition Task (PASAT): Participants are provided a string of single digit numbers on the computer and must add the total of the prior to integers presented and respond by selecting the answer using the computer mouse on the screen.

Participants will also be asked to provide an optional blood sample that will be banked with the Genetic Resources Core Facility. Samples will be analyzed at a later date and governed by a separate hypothesis-driven IRB protocol. Genetic sample collection will be optional and will not impact primary study eligibility.

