Optional Hair Analysis Substudy: Participants will be asked whether they would like to participate in a hair sampling substudy. The study will be considered optional to prevent disinterest in hair sampling from negatively impacting recruitment for the primary study. The rationale for this substudy is that hair analyses are emerging as an important method for detecting drugs use. This study can contribute valuable information to efforts to refine hair analyses because it administers drugs that have known abuse potential in a controlled manner and at known and uniform dose levels. The study PI has been asked by a NIDA Program Officer to collect hair samples from willing participants to be analyzed by the Neuroproteomics and Neurometabolomics Center at Northwestern University. Samples will be used to improve Maldi Sampling Techniques, to determine the degree to which accurate identification and quantification of levels of opioid and cannabinoid exposure in hair samples from individuals who are biologically confirmed to have no extra-study drug use is possible. Participants who are enrolled in the parent study will be asked about interest in this substudy and consented into the substudy via an oral consent procedure. The substudy will collect a hair sample at the beginning and end of the 6-week participation period. Samples will be collected via the commercially available Hair Test Collection Kit from Therapak and coded by participant ID numbers so that no PHI will be shared with the Center. Samples will be sent annually to the Center for analyses.

- b. Study duration and number of study visits required of research participants.

Participants will complete a Screening visit and 5 experimental session visits. Though sessions are expected to occur once weekly (for 5 weeks) participants will be able to extend sessions to greater than once per week if necessary, to accommodate potential scheduling barriers.

- c. Blinding, including justification for blinding or not blinding the trial, if applicable.

Participants and staff will be blinded to the doses of study medications being administered at each study visit. This will allow a rigorous test of the study hypotheses by not biasing participants or staff towards differential pain ratings.

- d. Justification of why participants will not receive routine care or will have current therapy stopped.

N/A

- e. Justification for inclusion of a placebo or non-treatment group.

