Hydromorphone (Dialudid) is a potent mu-opioid agonist that we have extensive experience administering in controlled laboratory settings. Hydromorphone is not subject to differences in CYP metabolic enzymes (in contrast to other opioids such as oxycodone) and therefore will not require us to screen out individuals with recent exposure to CYP inhibitors/inducers, or to analyze/statistically control for CYP metabolic profiles. We have selected a 4mg oral hydromorphone dose for this study because we have data from another ongoing study (IRB00047423) indicating it produces a mild-moderate effect (versus a ceiling or floor effect) and will therefore allow us to visualize changes as a function of the dronabinol. 4mg oral hydromorphone is also a dose that is commercially available and regularly prescribed for analgesia, which increases the clinical relevance of this study. Based on clinical experience, we expect it to produce a moderate analgesic effect on pain. This is an important feature because too strong a dose could overwhelm the cannabinoid effect and prevent us from effectively evaluating the study hypotheses. A moderate dose of hydromorphone will better enable us to evaluate shifts in the analgesic curve as a function of the study drug, and provide a stronger assessment of whether cannabinoids will enhance the analgesic effect of hydromorphone.

Study Drug Dosing		
Condition	Hydromorphone Oral	Dronabinol Oral
Nonrandomized 1	4mg	Placebo
Randomized 2	4mg	2.5mg
3	4mg	5mg
4	4mg	10mg
5	placebo	placebo
Session 1 will be nonrandomized and used as a safety screening day. Sessions 2-5 will be randomized and counter-balanced across participants.		

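### The stated blind at every visit does not, by design, cover dronabinol presence in the comparison with hydromorphone alone: for anyone who knows the schedule, Session 1 is known to be dronabinol-free

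*Combined protocol and SAP*

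**What the plan says.** Section 4.c claims that "Participants and staff will be blinded to the doses of study medications being administered at each study visit", and gives the reason: "This will allow a rigorous test of the study hypotheses by not biasing participants or staff towards differential pain ratings".

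Section 4.a (Project Overview) sets the order: "The order of sessions will be randomized with the exception of Session 1, which will always be active hydromorphone + placebo". The note under the dosing table in section 6.a agrees: "Session 1 will be nonrandomized and used as a safety screening day", and "Sessions 2-5 will be randomized and counter-balanced across participants". In that table the four randomized conditions are 4 mg hydromorphone with 2.5, 5 or 10 mg dronabinol, and a double placebo.

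Section 8.b says that research staff and participants are blinded to the exact medication, and that participants are not told which medication they receive. No section says that the Session 1 rule or the condition table is kept from session staff, and no assessment of the blind is planned. Among the session measures in section 4.a, "Pupil size will be assessed using an electronic Neuroptics Pupilometer"; section 8.a lists miosis among the side effects of hydromorphone.

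**The concern.** Capsule-level masking hides what is in a capsule. It cannot hide what follows from the position of a session. Hydromorphone alone occurs only in Session 1, so someone who knows the schedule can identify that condition without detecting any drug effect. In Sessions 2-5 such a person need not tell a cannabinoid effect from an opioid effect, because the only condition without dronabinol is inert.

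The affected comparison is central. Primary Aims 2 and 3 are framed against hydromorphone alone, and Aim 1 concerns adding dronabinol to hydromorphone. Several QST outcomes depend on a tester: pressure algometry, pinprick trains, von Frey border mapping and verbal pain ratings. A tester who expects more analgesia once dronabinol is present could shift these outcomes. Baseline correction does not remove an expectancy that acts after dosing, and a session-number covariate does not restore masking.

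**Working it through.** **1. Allocation structure.** Inputs are the five conditions in the section 6.a table, written as hydromorphone/dronabinol in mg: (4, 0), (4, 2.5), (4, 5), (4, 10), (0, 0). The first is fixed in Session 1 and the other four are permuted, so there are 4! = 24 permitted sequences. Over all 24:

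| Position | P(dronabinol) | P(hydromorphone alone) | P(dronabinol given active hydromorphone) |
|---|---|---|---|
| Session 1 | 0 | 1 | 0 |
| Each of Sessions 2-5 | 3/4 | 0 | 3/3 = 1 |

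For comparison, if all five conditions were randomized together, P(dronabinol given active hydromorphone) would be 3/4.

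**2. Imperfect recognition.** Section 6.a expects a mild to moderate effect from 4 mg, so recognition is not assured. Let *s* be the probability that an active session is perceived as active, and *f* the probability that the double-placebo session is. The documents give neither; I assume *s* from 0.5 to 1.0 and *f* from 0 to 0.3. By Bayes' rule, for Sessions 2-5:

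P(dronabinol given perceived opioid effect) = 3s / (3s + f)

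- s = 0.5, f = 0.3: 1.5 / 1.8 = 0.83
- s = 0.8, f = 0.1: 2.4 / 2.5 = 0.96
- f = 0, any s: 1.00

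Under full randomization the formula is 3s / (4s + f), which gives 0.65-0.75 over the same range. Session 1 needs no recognition at all.

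**3. What an expectancy shift could do (illustration).** The plan gives no SD, within-person correlation or expectancy size. I assume n = 60 (the completion target in section 4.a), correlation 0.5, and a normal approximation with unit SD.

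- SE of a paired contrast = √(2(1 − 0.5)/60) = 0.129 SD.
- Section 7.a specifies Tukey post-hoc tests. For five conditions the critical value on the z scale is about 2.75.
- Rejection per contrast = P(|Z + shift/0.129| > 2.75).

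| Assumed shift (SD) | Shift / SE | Rejection per contrast |
|---|---|---|
| 0 | 0 | 0.6% |
| 0.1 | 0.77 | 2.4% |
| 0.2 | 1.55 | 11.5% |
| 0.3 | 2.32 | 33.5% |

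With the 50 completers of section 7.c the SE is 0.141 SD, and the rates for the three shifts are about 2%, 9% and 26%. With three combination contrasts against Session 1, the chance of at least one rejection is higher than the per-contrast figure.

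**The case against.** A reader might infer that the blind cannot hold at all, and that any opioid sign in Sessions 2-5 reveals dronabinol with certainty. The documents do not support that. Unblinding needs both knowledge of the schedule and recognition of the effect. Section 8.b says that staff and participants are blinded to the exact medication. The consent pages were not available for review, so what participants learn about Session 1 is undetermined. That staff know the schedule is inferred from the protocol's silence. Section 5 does list failure to discriminate hydromorphone from placebo as an exclusion, which would favour recognition. However, it ties this to a second screening or qualifying session that the visit schedule in section 4.b does not contain.

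A reader might also infer that all three primary aims are compromised. That goes too far. Knowing only that dronabinol is present cannot by itself produce a gradient across 2.5, 5 and 10 mg, and Aim 1 predicts a dose-dependent effect. The Aim 3 tests are computer-based, and heat tolerance ends with the participant's own button press. The Aim 2 money rating comes from the participant, so bias there requires that participants know the Session 1 rule.

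Finally, one might compute false-positive rates of 12%, 34% and 64% for the same shifts with an unadjusted two-sided 5% test. The plan specifies Tukey tests for the QST outcomes, so those rates do not apply.

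What remains is that section 8.b repeats that the medication is undisclosed, which does not help against someone who knows the fixed order. Section 4.a also uses Session 1 to confirm a safe response to hydromorphone. Someone must therefore know its content, and the plan does not say who.

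**Conclusion.** The concern holds as a conditional weakness of the blind. Section 4.c claims a property at every visit that the design does not provide for dronabinol presence in the contrast with hydromorphone alone. The allocation result (0 in Session 1; 3/3 given active hydromorphone in Sessions 2-5) is exact and follows from section 6.a. The 0.83-1.00 range rests on assumed detection rates. The rejection rates rest on assumed shifts, SD scale and correlation; they illustrate sensitivity and are not evidence of actual bias.

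The exposure lies mainly in staff-run and verbally rated QST measures, if staff know the schedule. Comparisons among the three dronabinol doses are not affected by this point. The confounding of hydromorphone alone with session order is a separate problem.

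**What to change.** 1. Restate section 4.c: the blind covers which dronabinol dose is given in Sessions 2-5, but does not by design cover dronabinol presence relative to Session 1. Carry that limit into the interpretation of the combination versus hydromorphone-alone contrasts.
2. Restrict the Session 1 rule and the condition table to pharmacy and the responsible medical staff, and keep them from those who run QST and collect ratings. If this is already the practice, write it into the protocol.
3. Hide pupil readings from the QST tester throughout the session. Running QST before pupillometry within a block is not enough, because the measures repeat through the day.
4. Give participants and raters accurate, neutral wording, subject to ethics review: the study uses an opioid, a cannabinoid and placebo, and the content of a given session is not disclosed. Do not say that any session may contain any combination; under section 6.a that is untrue, because Session 1 never contains dronabinol and no session gives dronabinol alone.

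The cost is staff briefing, ethics review of the wording and separate handling of pupil data, with no added visits. Session staff would work from a less specific schedule, and the blinding statement becomes less favourable. Sedation and other visible effects would remain as cues. None of these steps removes the confounding of hydromorphone alone with session order.
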